8.4 Sensitivity Analyses of Chair Rise Rate

As a sensitivity analysis, the primary analysis will be conducted excluding participants who enrolled into PREPARE after REPRIEVE entry (i.e. participants who enrolled into PREPARE retrospectively and do not have pre-treatment chair rise rate available). These sensitivity analyses will not be conducted for the subgroup analyses, but they may be considered should there be a substantial difference found in the results of the primary treatment effect analysis.

8.5 Analyses of Secondary Physical Function Outcomes

This section describes analyses of the secondary physical function and activity outcomes listed in Section 4.2.

8.5.1 Analysis Data

Available outcome data with the exception of PREPARE entry evaluations performed after initiation of study treatment not used for baseline. The evaluations will be separated into baseline, and months 12, 24, 36 and 48 as specified in Section 6.4. In the linear mixed effects model and cumulative logit model, all evaluations will be used regardless of participants time of entry into PREPARE and visit windows.

8.5.2 Analytic Methods

For the secondary outcomes (including gait speed, grip strength, composite mSPPB ratio and balance ratio), linear mixed effects modeling approach as described for the primary analysis (Section 8.2.2) will be used, if appropriate, given the data distributions. This will provide estimates of the difference in the rate of change (slope) in gait speed (meters/second per year) and grip strength (kg per year) between placebo and pitavastatin over time. For some outcome measures (e.g. composite mSPPB ratio and balance ratio), log-transformation may be used to provide estimates of annual change in percent scale.

Treatment group differences in the prevalence of the frailty phenotype (non-frail, pre-frail, frail) will be assessed via marginal modeling with a cumulative logit using generalized estimating equations. Proportional odds approach which extends inference to underlying continuum and is invariant with respect to choice of response categories will be used.

Similarly to the primary analysis of linear mixed effects model (Section 8.2.2), time will be modeled on a continuous scale, where REPRIEVE entry is time 0 and the model will include intercept, the main effect of time and the interaction of time and treatment group, and omit the main effect of treatment group (intercept). Exchangeable correlation structure will be used for repeated measurements within participant. The main parameter of interest is the difference in the rate of change (slope) between placebo and pitavastatin over time (i.e., the interaction between treatment and time).

Given the discretized distribution of the remaining physical function secondary outcomes (including the composite SPPB score and overall DASI score), Wei and Johnson method will be used to assess the overall difference between treatment groups over time.

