6.3.3 REAP Questions #26 and #27

These questions will be administered at 12, 36, 48, **and 60** months, and **at** discontinuation as a measure of self-reported physical activity; these assessments are obtained at entry in REPRIEVE (A5332) and at month 24 in A5333s. In the event that **the A5361s entry visit coincides with the month 12 visit for A5332 or A5333s**, REAP questions #26 and #27 will be completed as part of a **combined A5361s entry and A5332/A5333s month 12 visit**.

For REPRIEVE (A5332) participants not enrolled in A5333s, REAP questions #26 and #27 at month 24 will also be completed as part of A5361s.

The questions are as follows: In an average week, how often do you: (usually/often, sometimes, rarely/never, does not apply):

- #26 Do less than 30 total minutes of physical activity 3 days a week or more? (Examples: walking briskly, gardening, golf, jogging, swimming, biking, dancing, etc.)
- #27 Watch more than 2 hours of television or videos a day?

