These primary analyses will be extended to evaluate subgroup effects of treatment, namely different treatment effects by race (white vs non-white), sex, baseline CD4 cell count (<350 cell/mm vs. \geq 350 cells/mm), ART duration (categorized as <10 or \geq 10 years), physical function deficits at REPRIEVE (A5332) entry (SPPB \leq 10 vs. $>$ 10), and systemic inflammation (by tertile of IIS) at REPRIEVE (A5332) entry. Sensitivity analyses excluding participants who enrolled into A5361s after REPRIEVE (A5332) entry will also be performed.

Given the expected discretized distribution of the remaining SPPB outcomes (including the overall composite score), longitudinal analyses for these measures as well as the self-reported physical function outcomes from the REAP assessment will use the methods of Wei and Johnson to provide an overall assessment of treatment group differences between the groups over time.

The prevalence of the frailty phenotypes and their components over time and by treatment group will be described. Treatment group differences in the prevalence of the frailty phenotype (non-frail, pre-frail, frail) will be assessed via marginal modeling with a cumulative logit using generalized estimating equations.

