- Grip strength (kg) in the dominant hand (average of the results will be used).

Self-Reported Physical Activity and Capacity Outcome Measures [1.3.4]

- Self-reported physical activity via two questions measured on a three-point ordinal scale (usually/often, sometimes, rarely/never) on the Rapid Eating and Activity Assessment for Patients (REAP) assessment. In an average week, how often do you:
 - do less than 30 total minutes of physical activity 3 days a week or more? (Examples: walking briskly, gardening, golf, jogging, swimming, biking, dancing, etc.) [REAP question 26].
 - watch more than 2 hours of television or videos a day? [REAP question 27].
- Self-reported physical capacity measured by the overall score of Duke Activity Status Index (DASI) as described by Hlatky et al. [*Am J Cardiol.* 1989 Sep 15;64(10):651-4.]. Evaluated at REPRIEVE entry and at month 24.

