5 DATA SOURCES FOR OUTCOME MEASURES

The data and samples from the main study REPRIEVE, the mechanistic substudy A5333s and PREPARE will be used as shown in the table below.

Outcome Measure	REPRIEVE (A5332) Entry	Year 1	Year 2	Year 3	Year 4
Physical function battery	A5361s ¹	A5361s ²	A5361s	A5361s	A5361s
Frailty components	A5361s ¹	A5361s ²	A5361s	A5361s	A5361s
Duke Activity Status Index (DASI)	A5332 ³		A5333s/A5361s ⁴		
Self-reported physical activity and sedentary time (REAP) ⁵	A5332 ³	A5361s ²	A5333s/A5361s ⁴	A5361s	A5361s
Myalgia symptom assessment	A5332 ³	A5332 ³	A5332	A5332	A5332
Samples for inflammatory markers	A5332 ³	A5332 ³			
Fasting lipids and insulin sensitivity	A5332/A5333s ³		A5332/A5333s		
CT scan for fatty infiltration and muscle mass of the skeletal trunk muscles	A5333s ³		A5333s		

¹Will be available only to participants who enroll concurrently into REPRIEVE (A5332) and A5361s. For participants who enroll into PREPARE after REPRIEVE entry, evaluation will be conducted at PREPARE entry also.

²Will be available only to participants who enroll into A5361s concurrently or within 12 months of REPRIEVE (A5332) entry. For participants who enroll into PREPARE after REPRIEVE entry, evaluation will be conducted at PREPARE entry also.

³For participants who enroll into A5361s after REPRIEVE (A5332) entry, the data and samples collected in REPRIEVE and A5333s prior to A5361s entry will be used.

⁴For participants not enrolled into A5333s, collected as part of A5361s.

⁵Questions 26 and 27 only.

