6 GENERAL ANALYSIS CONSIDERATIONS

6.1 Baseline

Baseline will be defined as the REPRIEVE entry evaluation. The baseline characteristics derived for the main study REPRIEVE will be used, if available. For the physical function and frailty measures, baseline is defined as PREPARE entry evaluation prior to or on the day of the study treatment initiation in REPRIEVE. As such, participants who enroll into PREPARE after initiation of study treatment in REPRIEVE, will not have a baseline (pre-treatment) evaluation.

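### SAP 8.5.2 does not say how the REPRIEVE-entry REAP and DASI values enter the Wei-Johnson tests; adjusting the overall comparison for them would gain precision at no cost in data

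*SAP*

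**What the plan says.** **Test.** SAP 8.5.2 states that for the "remaining physical function secondary outcomes (including the composite SPPB score and overall DASI score), Wei and Johnson method will be used", and the same sentence gives the purpose: "Wei and Johnson method will be used to assess the overall difference between treatment groups over time". REAP is not named there but falls among the remaining outcomes. Protocol 10.6.1 names it: the "self-reported physical function outcomes from the REAP assessment will use the methods of Wei and Johnson".

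**Entry values.** SAP 6.1 states: "Baseline will be defined as the REPRIEVE entry evaluation". SAP 4.2 gives the DASI schedule as "Evaluated at REPRIEVE entry and at month 24". Of the REAP items, Protocol 6.3.3 says that "these assessments are obtained at entry in REPRIEVE (A5332) and at month 24 in A5333s". In the SAP section 5 table, the REAP and DASI entry cells carry footnote 3. For participants who join PREPARE after REPRIEVE entry, it says that "the data and samples collected in REPRIEVE and A5333s prior to A5361s entry will be used". A pre-treatment value is therefore planned for everyone.

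**Role of the entry value.** SAP 8.5.1 says: "The evaluations will be separated into baseline, and months 12, 24, 36 and 48 as specified in Section 6.4". Neither document says whether baseline is a covariate in the Wei-Johnson test, one of its time points, or used only for description.

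**Other outcomes.** SAP 9.3 adjusts the biomarker and CT comparisons for baseline. The mixed models and the frailty model place REPRIEVE entry at time 0 and use the entry observation as an outcome.

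**The concern.** In SAP section 4, only REAP and DASI are tagged to objective 1.3.4, the effect of pitavastatin on self-reported activity. A person's own pre-treatment answer usually predicts later answers, and here it is already in the parent trial's database.

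The text allows two natural readings, and neither uses that value well. If baseline stays out of the test, DASI under the SAP schedule becomes a two-sample rank comparison at month 24. If baseline is one of the times combined in the test, a measurement that treatment cannot have affected is averaged into the treatment effect. At stake is avoidable imprecision on objective 1.3.4, and an analyst's choice that should be fixed before unblinding.

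**Working it through.** **Inputs**
- n = 300 per group (Protocol 10.4.2).
- Two-sided 5% (SAP 6.7, stated for the primary outcomes; assumed here).
- Correlation ρ: the only documented value is 0.6, for chair rise (Protocol 10.4.1). None is given for REAP or DASI, so I use 0.3 to 0.7.
- Effect d = 0.2 SD at every post-entry visit: an assumption.
- Follow-ups m: DASI 1 and REAP 4 under the SAP; DASI 2 and REAP 5 under Protocol Version 2.0.
- Exchangeable correlation, equal weights and complete data: assumptions.

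**Formula check.** The documents give no power figure for REAP or DASI. The biomarker statement in Protocol 10.4.2 (0.28 SD, 10% inevaluable, so 270 per group) gives 0.28/√(2/270) = 3.25 and Φ(3.25 − 1.96) = 90.2%. This matches the stated 90%.

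**1. Variance of the post-entry mean**

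Unadjusted: V_u = (1 + (m−1)ρ)/m. Adjusted for entry: V_a = V_u − ρ².

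For m = 4 and ρ = 0.6, V_u = 2.8/4 = 0.70, V_a = 0.70 − 0.36 = 0.34, and the ratio is 0.49.

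| V_a/V_u | ρ=0.3 | 0.4 | 0.5 | 0.6 | 0.7 |
|---|---|---|---|---|---|
| DASI, m=1 | 0.91 | 0.84 | 0.75 | 0.64 | 0.51 |
| DASI, m=2 | 0.86 | 0.77 | 0.67 | 0.55 | 0.42 |
| REAP, m=4 | 0.81 | 0.71 | 0.60 | 0.49 | 0.37 |
| REAP, m=5 | 0.80 | 0.69 | 0.58 | 0.47 | 0.36 |

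**2. Power, Φ(d/√(2V/n) − 1.96)**

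With V = 1, 0.2/√(2/300) = 2.449.
- DASI, m=1, unadjusted: Φ(0.489) = 69% at any ρ.
- DASI adjusted: 2.449/√0.91 = 2.57, so 73% at ρ = 0.3; 2.449/√0.64 = 3.06, so 86% at ρ = 0.6.
- REAP, m=4, ρ = 0.3: 94.5% unadjusted (V = 0.475), 97.7% adjusted (V = 0.385).
- REAP, m=4, ρ = 0.6: 83.3% unadjusted (V = 0.70), 98.7% adjusted (V = 0.34).

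**3. Entry counted as a time point**

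The effect becomes d·m/(m+1) and the variance (1 + mρ)/(m+1). At ρ = 0.6:
- DASI: 0.10/√(2×0.8/300) = 1.37, so power falls from 69% to 28%.
- REAP: 0.16/√(2×0.68/300) = 2.38, so power falls from 83% to 66%.

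**4. Three-level outcome**

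Simulation with 270 per arm and 4,000 replicates, comparing equal-weight combined rank scores with the same scores adjusted for entry rank. The latent effect was 0.28 SD with one visit and 0.22 SD with four.

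| Latent ρ (observed rank correlation) | One visit | Four visits |
|---|---|---|
| 0.3 (0.24) | 84.0% → 86.1% | 94.4% → 96.8% |
| 0.6 (0.50) | 82.0% → 92.2% | 82.8% → 96.0% |

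Under the null (four visits, latent ρ 0.6), rejection was 4.8% unadjusted and 5.2% adjusted.

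**5. Would the frailty model serve for REAP?**

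That model tests a time-by-treatment slope with a common intercept. Normal approximation by generalized least squares, visits at years 0 to 4, 300 per arm, constant 0.2 SD post-entry effect:

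| ρ | Unadjusted average | Slope model | Adjusted average |
|---|---|---|---|
| 0.3 | 94.5% | 90.8% | 97.7% |
| 0.4 | 91.0% | 88.9% | 97.5% |
| 0.6 | 83.3% | 90.0% | 98.7% |

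For a constant effect, the slope model loses to the unadjusted average at low ρ. The adjusted average gains at every ρ tried.

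**The case against.** **The plan does not say that baseline is dropped.** This is correct. A reader might infer from SAP 8.5.2 that the entry value goes unused, but SAP 8.5.1 keeps baseline in the analysis data, and SAP section 1 leaves coding details to a separate Analysis Implementation Plan. What stands is that its role is undefined.

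**REAP and DASI are not singled out.** A reader might infer that they alone miss an adjustment given everywhere else. The same SAP sentence sends the composite SPPB score to Wei-Johnson, and other discretized outcomes follow under remaining outcomes. What sets REAP and DASI apart is that their entry value is planned for late joiners too. For the physical function battery it is not (SAP 6.1).

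**The gain may be small.** A reader might infer a large loss of power. The documents give no REAP or DASI correlation, and 0.3 is plausible for a single three-level item; the simulated gain there is about 2 points. Late joiners also have fewer REAP visits than the four assumed.

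**Not every entry value will be usable.** REAP has a does-not-apply answer (Protocol 6.3.3) outside the three-point scale in SAP 4.2, and ordinary missing data will occur.

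**The test is valid and the outcomes are secondary.** Both are true, and SAP 6.7 promises cautious interpretation. This limits the weight of the point but gives no reason to leave a prognostic covariate without a role.

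**Conclusion.** The point holds as a free improvement and a needed clarification, not as an error. SAP 8.5.2 and Protocol 10.6.1 assign REAP and DASI to an overall Wei-Johnson test with no stated use of an entry value that is planned for all participants. Adjustment would cut the variance by 9% (ρ = 0.3) to 36% (ρ = 0.6) for one DASI follow-up, and by 19% to 51% for four averaged REAP visits. For an assumed 0.2 SD effect with 300 per arm, this is worth about 4 to 18 power points for DASI and 3 to 15 for REAP. The gain is modest if ρ is near 0.3 and substantial from about 0.5. These sizes rest on assumed correlations, a constant effect and complete data. Treating entry as a combined time point is the one reading that would do real damage. Type I error is not in question.

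**What to change.** In SAP 8.5.2, for REAP 26, REAP 27 and DASI:

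1. Keep the overall, average post-entry treatment comparison, and adjust it for the REPRIEVE-entry value. Covariate-adjusted rank scores (rank ANCOVA) would do this. So would a repeated-measures proportional-odds model with the entry response as a covariate and an average treatment effect.
2. State that the REPRIEVE-entry value is a covariate and never one of the time points combined in the treatment test.
3. Apply this to every post-entry assessment. Protocol Version 2.0 adds a month-60 REAP and a later DASI taken from the REPRIEVE month-96 or termination visit. The SAP rests on Version 1.0 and includes neither.
4. Do not replace the overall REAP test with the slope-only frailty model.
5. Say how missing or does-not-apply entry answers are handled, so that these participants stay in the comparison.

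The unadjusted Wei-Johnson result can be kept as supportive. The cost is a few lines of SAP text, settled before unblinded analysis. No new data are needed, because the entry REAP and DASI come from A5332.

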9 EFFECT OF PITAVASTATIN ON INFLAMMATION/IMMUNE ACTIVATION AND SKELETAL TRUNK MUSCLE

This section outlines analyses for the outcomes addressing the secondary objectives 1.3.2 and 1.3.6, and for the effect of pitavastatin on mechanistic biomarker outcomes which are not described in A5333s. Refer to Section 4 for the list of outcome measures.

9.1 Analysis Considerations

The analyses of mechanistic biomarker and fatty infiltration outcomes will be AT, as defined in Section 6.5.

Descriptive statistics (number of observations, mean and standard deviation, median (Q1 – Q3), P10 – P90, minimum – maximum) and graphical presentations over time will be provided.

9.2 Analysis Data

Outcome measure results at baseline and post-baseline on-treatment results. Results after treatment interruptions for extended period of time (to be defined) will also be excluded (Section 6.5). The evaluations will be separated into baseline, and month 12 for biomarkers or month 24 for CT outcomes (fatty infiltration and muscle mass) as specified in Section 6.4. The analyses of the CT outcomes include (1) all A5333s participants with results available (i.e. including those not enrolled into PREPARE) (2) participants co-enrolled into PREPARE and A5333s with results available.

9.3 Analytic Methods

Pointwise treatment group comparisons will use linear regression adjusted for baseline to provide estimation of the difference in the baseline-adjusted level of the outcomes at the follow-up visit. Outcome transformations will be applied as appropriate. Treatment group comparisons of markers of inflammation and immune activation will be limited to those not described in A5333s. For the CT outcomes, the primary treatment comparisons are on all participants with the muscle function data (i.e. including those not enrolled into PREPARE). The analysis will also be conducted among the participants enrolled into PREPARE to ensure a consistent effect size. Unless a test for heterogeneity of effect (interaction between enrollment into PREPARE and treatment effect) suggests otherwise, the PREPARE cohort effect sizes will be presented to give content to the main findings, but inference will be made on the full cohort.

Analyses of CT outcomes will also assess the association of these changes with changes in lipid components and HOMA-IR as listed below. The linear regression for treatment group comparison described above will be expanded to evaluate each lipid component and HOMA-IR separately.

- Lipid components including LDL cholesterol and triglycerides
- HOMA-IR calculated as [glucose (mg/dL) x insulin (uIU/mL)]/ 405

10 MECHANISTIC PATHWAYS THROUGH WHICH PITAVASTATIN AFFECTS PHYSICAL FUNCTION

This section outlines analyses for the outcomes addressing the primary objective 1.2.2, secondary objectives 1.3.3, 1.3.5, and exploratory objectives 1.4.1 and 1.4.2. The primary physical function outcome measure of chair rise rate and all mechanistic biomarker and fatty infiltration outcome measures will be used (Section 4).

10.1 Analysis Considerations

The analyses will be ITT, as defined in Section 6.5.

10.2 Analysis Data

The results for the primary physical function outcome, chair rise rate, will be used. Biomarker and CT outcome results from baseline and post-baseline (month 12 or month 24 for biomarkers and CT, respectively). The analyses using biomarker outcomes from A5333s and CT outcomes are limited to participants who were co-enrolled in A5333s.

10.3 Analytic Methods

The relationship between markers of inflammation/immune activation, fatty infiltration, and physical function will be assessed via longitudinal modeling of the chair rise rate (dependent variable) and expanding each of the appropriate models used to assess treatment group difference including baseline and post-baseline biomarker and fatty infiltration outcomes. Directed acyclic graphs (DAGs) will be used to describe the assumed causal relations among the biomarkers, fatty infiltration outcomes, other potential covariates (see below), and chair rise rate to guide in covariate selection.

The analyses will also examine associations with the following measured covariates/risk factors:

- Demographic and behavioral variables (age, race, sex, BMI, smoking, alcohol use, physical activity by REAP)
- Co-morbid conditions (HBV/HCV, hypertension, diabetes mellitus, chronic kidney disease)
- Menopausal status and sex hormones (total and free testosterone), for women only; depending on the number of women enrolled
- Baseline vitamin D level
- Use of angiotensin-converting-enzyme inhibitor/angiotensin II receptor blocker (ACE-I/ARB) therapy
- HIV-related variables (CD4 cell count [nadir and current]), HIV RNA, antiretroviral exposure (cumulative and current exposure to ART)
- Muscle symptoms (via the myalgia symptom assessment collected through REPRIEVE)

- Concomitant medications, specifically, ACE-I/ARB therapy and use of hormonal therapy

Given the assumed temporal associations under study, the analyses will consider only including dependent outcomes assessed from month 24 onward. These analyses will be considered with and without adjustment for treatment assignment to allow assessment of the degree to which the effects of treatment might be mediated through treatment-associated changes. While further, more formal causal mediation analyses are planned, given the expected statistical developments in the relevant statistical methodology over the next 4 years, these analysis plans will be developed closer to the time of analysis.
